7.1.2 Definition of continuous exposure, discontinuation, switch or add-on

The continuous exposure periods of index drug have been created by linking all prescriptions with days of supply with 30 days grace period in between. Note: 30 days grace period is used in main analysis. 90 days grace period will be used in sensitivity analysis. The discontinuation is when there is more than 30 days gap from current prescription exposure end to next prescription date. The discontinuation date is 30 days after the end of days of supply of the last prescription date.

Addition of a new medication means when the prescription date of this new medication is before the last prescription date of the index continuous exposure. The prescription date of new medication is add-on date.

Switch to new medication means the prescription date of this new medication is on or after the last prescription date of the index continuous exposure and before the end of discontinuation. The prescription date of new medication is switch date. Different scenarios for switch, discontinue, or add on were mentioned in the study protocol.

7.1.3 Definition the censored follow-up end

The study will be conducted utilizing a modified “as-treated” approach. The follow up time starts from index date till the earliest date of these following events:

1. Discontinuation of index drug.
2. Switch or add-on the within treatment line comparator (other SGLT2 in empagliflozin group or the comparator group. Please refer to [Table 1](#) for different switch or add-on scenarios for each group.
3. Outcome: AP event. The first date of AP event is the event date.
4. The minimum date of death date or enrollment end date or study end date

As long as it is not the treatment line comparator, patients are allowed to add a non-incretin/non-SGLT2i hypoglycemic agent to their index therapy and can also switch to non-incretin/non-SGLT2i hypoglycemic agents.

Based on the feasibility studies, the patients having fixed dose of Empagliflozin + Metformin are defined as dual Empagliflozin patients. The index date is the first prescription of fixed dose prescription.

For the patients starting Metformin then Empagliflozin, these patients are free dose Empagliflozin + Metformin dual patients and they are defined as dual Empagliflozin patients by following exposure group definition process. The index date is the first Empagliflozin prescription date.

For both situations, the index drug is Empagliflozin. The censor date will be captured by following the same rule.

Proprietary confidential information © 2022 Boehringer Ingelheim International GmbH or one or more of its affiliated companies

Censoring Event as the End of Study Period

Only look for the **censor events** during the **first continuous exposure of index drug**.

The **discontinuation of index drug** is the end of **first continuous exposure of index drug**, which is the 30 days after the last days of supply.

Version of databases : Optum: Q1, 2021; [REDACTED] CCAE: Q3, 2020

08.2014

[figure not shown]

Figure 2

Diagram for definition of the censored end of follow up

7.2 OUTCOMES

Please check section 9.3.2. of the study protocol.

7.3 COVARIATES

Please check section 9.3.3. of the study protocol. List of covariates and operational definitions are added to [Annex 3](#).

8. DATA SOURCES

Please check section 9.4 of the study protocol.

9. DATA MANAGEMENT AND SOFTWARE/TOOLS

Data is stored using the secured Instant Health Data (IHD) platform (<https://www.bhei.com/product>). Access to the data is granted by password to trained, BI personnel only. All study details are addressed either in the protocol, SEAP, or DMRP.

9.1 SOFTWARE/TOOLS

The cohort selection part will be conducted in IHD platform and the data analysis will be run in BI internal server using SAS software 9.4 ([REDACTED]) or R Studio 3.5.2.

9.2 HANDLING OF MISSING VALUES

The absence of a code for a condition will be interpreted as an absence of the event. If a study variable is totally missing from a database, it is excluded from the analysis of the pooled data. If a variable is missing for only some of the patients a missing data category will be added and utilized in the analysis.

9.3 HANDLING OF INCONSISTENCIES IN DATA AND OUTLIERS

For lab values, distribution of each variable will be assessed. The extreme outliers will be treated as missing values approaches to handling missing values are described in the previous section.

10. DATA ANALYSIS

10.1 DEFINITIONS

Please check the study protocol section 9.7.1.

10.2 PROPENSITY SCORE

Please check study protocol section 9.7.2.

10.3 MAIN ANALYSIS

Please check study protocol section 9.7.3.

10.4 META-ANALYSIS

Please check study protocol section 9.7.4.

BOEHRINGER INGELHEIM Group of Companies
Statistical and Epidemiological Analysis Plan (SEAP) for Non-
Interventional Studies (NIS)

c37922104-02

Page 13 of 27

Proprietary confidential information © 2022 Boehringer Ingelheim International GmbH or one or more of its affiliated companies

BOEHRINGER INGELHEIM Group of Companies
Statistical and Epidemiological Analysis Plan (SEAP) for Non-
Interventional Studies (NIS)

c37922104-02

Page 14 of 27

Proprietary confidential information © 2022 Boehringer Ingelheim International GmbH or one or more of its affiliated companies

10.6 SENSITIVITY ANALYSIS

See relevant section of the study protocol.

10.7 SAFETY ANALYSIS

Not applicable based on secondary use of data without any potential that any employee of BI or agent working on behalf of BI will access individually identifiable patient data.

11. QUALITY CONTROL

The quality control, review, and monitoring plan are summarized below. Greater details are documented in the NIS-DMRP.

All measures created, cohorts developed, statistical analyses implemented, and tables completed will be conducted by two analysts independently. After completing the whole analysis, each analyst will undergo quality control review for the other analyst's work. The final results need to be consistent results from both analysts.

This protocol will be strictly followed in the study. All changes to this protocol will be documented in protocol amendments.

All programs for data management and data analyses written by study statistician(s) will be self-documenting with comments about the data handling process, the population selection and the analysis performed by the program. The documentation will be sufficient for another statistician to be able to repeat the program. A statistician other than the one who writes the program will carry out quality control checks of these programs. The programming quality control (QC) will be performed for all programs related to the database, its individual datasets from different registers and statistical analyses. The QC will be documented with the following information:

- Name of the program
- Purpose of the program
- Name of the programmer
- Validation status and date of validation
- Updates and dates of updates
- Name of the QC statistician
- QC findings or comments
- Date of QC

The statistician responsible for the QC of a program will ensure that:

- The correct dataset and population has been used
- The analysis is carried out according to the SEAP
- The analysis results are consistent

BOEHRINGER INGELHEIM Group of Companies
Statistical and Epidemiological Analysis Plan (SEAP) for Non-Interventional Studies (NIS)

c37922104-02

Page 16 of 27

Proprietary confidential information © 2022 Boehringer Ingelheim International GmbH or one or more of its affiliated companies

- The output is in line with the table shells in the SEAP
- The analysis can be interpreted in both statistical and clinical terms.

All QC findings by the QC statistician will be documented, and corrections are made to the programs accordingly. All changes are documented as updates to the original program.

The raw dataset and statistical programs used for generating the data included in the final study report will be kept in electronic format and be available for auditing and inspection.

ANNEX 1. LIST OF ICD 9 AND ICD 10 CODES FOR COHORT CREATION

Condition	ICD 9 codes ¹	ICD 10 codes ²
T1DM	250.X1, 250.X3	E10.xx
T2DM	250.X0, 250.X2	E11.xx
Gestational diabetes	648.8x	O24.1x, O24.4x
Secondary diabetes	249.xx	E08.xx, E09.xx, E13.xx
Acute pancreatitis	577.0	K85.xx
Chronic pancreatitis	577.1	K86.1 Other chronic pancreatitis
Pancreatitis cancer	157.xx	C25.xx
Other disease of pancreatitis	577.2, 577.8, 577.9	K86.2, K86.3, K86.8x, K86.9

1. 2015 ICD-9-CM Diagnosis Codes: <http://www.icd9data.com/2015/Volume1/default.htm> accessed at 14 March 2020

2. 2019 ICD-10-CM Codes: <https://www.icd10data.com/ICD10CM/Codes> accessed at 14 March 2020

ANNEX 2. MEDICATION CODES USED TO DEFINE EXPOSURES AND EXCLUSION CRITERIA OR CENSORING

Medication Class / Generic (Brand) Name
Medication for Exposure Groups Definition
Empagliflozin
Empagliflozin (Jardiance): Empa Mono
Empa+ Met
Metformin + Empagliflozin (Synjardy): Empa Dual
Metformin + Empagliflozin extended-release (Synjardy XR): Empa Dual
Metformin
Metformin (Glucophage, metformin hydrochloride, Fortamet, Glumetza, Riomet): Metf Mono
Met + TZD
Metformin + Pioglitazone (Actoplus Met): Metf + TZD
Metformin + Rosiglitazone (Avandamet): Metf + TZD
Met + SU
Metformin + Glipizide (Metaglip): Metformin and SU Dual
Metformin + Glyburide (Glucovance): Metformin and SU Dual
SU (Combine 1st and 2nd gen)
Glimepiride (Amaryl)
Glipizide (Glucotrol)
Glyburide (DiaBeta)
Glynase
Glycron
Micronase
Acetohexamide (Dymelor)
Chlorpropamide (Diabinese)
Tolazamide (Tolinasel)
Tolbutamide (Orinase)
TZD
Alogliptin + Pioglitazone (Oseni)
Pioglitazone (Actos)
Rosiglitazone (Avandia)
SU+ TZD
Glimepiride + Rosiglitazone (Avandaryl)
Glimepiride + Pioglitazone (Duetact)

BOEHRINGER INGELHEIM Group of Companies
Statistical and Epidemiological Analysis Plan (SEAP) for Non-Interventional Studies (NIS)

c37922104-02

Page 21 of 27

Proprietary confidential information © 2022 Boehringer Ingelheim International GmbH or one or more of its affiliated companies

Medication used in exclusion or censoring exposure duration:
Dipeptidyl peptidase-4 inhibitor (DPP-4i)
Alogliptin (Nesina)
Metformin + Alogliptin (Kazano)
Linagliptin (Tradjenta)
Metformin + Linagliptin (Jentadueto)
Empagliflozin + Linagliptin (Glyxambi)
Saxagliptin (Onglyza)
Metformin + Saxagliptin (Kombiglyze)
Sitagliptin (Januvia)
Metformin + Sitagliptin (Janumet)
Sitagliptin + Simvastatin (Juvisync)
Glucagon-like peptide-1 receptor agonist (GLP-1 RA) with Insulin
Albiglutide (Tanzeum)
Dulaglutide (Trulicity)
Exenatide (Byetta, Bydureon)
Rybelsus (Semaglutide)
Xultophy (insulin degludec and liraglutide injection)
Glargine + Lixisenatide (Soliqua)
Liraglutide (Victoza, Saxenda)
Lixisenatide (Adlyxin)
Semaglutide (Ozempic)
Sodium-glucose cotransporter-2 inhibitors (SGLT-2i mono and combi)
Canagliflozin (Invokana)
Metformin + Canagliflozin (Invokamet)
Metformin + Canagliflozin extended-release (Invokamet XR)
Dapagliflozin (Farxiga)
Empagliflozin (Jardiance)
Empagliflozin + Linagliptin (Glyxambi)
Metformin + Empagliflozin (Synjardy)
Metformin + Empagliflozin extended-release (Synjardy XR)
Dapagliflozin + Saxagliptin (Qtern)
Metformin + Dapagliflozin extended-release (Xigduo XR)
Ertugliflozin (Steglatro)
Ertugliflozin + Metformin (Segluromet)
Ertugliflozin + Sitagliptin (Steglujan)
Insulin

ANNEX 3. STUDY COVARIATES

N	Category	Variables	Definition
1	Demographics	Age	
 - By year - By category (18-54, 55-64, 65-74, 75+)
		Gender	
 - Male, Female
		Smoking	
All codes could be found in the following excel file:
  
1245-0201%20codes%20part%201_03022

		Alcohol abuse or dependence	
		Drug abuse or dependence	
		Overweight	
		Obesity	
		Calendar quarter of cohort entry	
2	Comorbidity indexes	Elixhauser comorbidity index	
 - R14-4775
		Charlson comorbidity index	
3	Diabetes specific complications	Diabetes retinal problems	
Diabetic retinopathy, diabetes with other ophthalmic manifestations, Retinal detachment, vitreous hemorrhage, vitrectomy, retinal laser coagulation therapy. Codes presented in the following excel file:
  
1245-0201%20codes%20part%201_03022

		Diabetic neuropathy	
		Diabetic nephropathy	
		Hypoglycaemia	
		Hyperglycaemia	
		Disorders of fluid electrolyte and acid-base balance	
		Diabetic ketoacidosis	
		Hyperosmolar hyperglycemic nonketotic syndrome (HONK)	
		Diabetes with peripheral circulatory disorders	
		Diabetic foot	
		Gangrene	
		Lower extremity amputation (lower extremity amputation diagnosis code, lower extremity amputation procedure code (ICD), lower extremity amputation procedure code (CPT).)	
		Osteomyelitis	
		Skin infections	
		Erectile dysfunction	
		Diabetes with unspecified complication	
		Diabetes mellitus without mention of complications	

BOEHRINGER INGELHEIM Group of Companies
Statistical and Epidemiological Analysis Plan (SEAP) for Non-Interventional Studies (NIS)

c37922104-02

Page 23 of 27

Proprietary confidential information © 2022 Boehringer Ingelheim International GmbH or one or more of its affiliated companies

4	General medical history	Hypertension	Codes presented in the following excel file:  1245-0201%20codes%20part%202_03022
		Hyperlipidaemia	
		Myocardial infarction (Acute MI and old MI)	
		Angina (ACS/unstable angina, stable angina)	
		Coronary atherosclerosis and other forms of chronic ischemic heart disease	
		Cardiac procedures (Previous cardiac procedure (CABG or PTCA or Stent))	
		Ischemic stroke (w and w/o mention of cerebral infarction)	
		Hemorrhagic stroke	
		TIA	
		Cerebrovascular disease (Other cerebrovascular disease, late effects of cerebrovascular disease, Cerebrovascular procedure)	
		Heart failure (CHF)	
		Peripheral Vascular disease or PVD surgery	
		Atrial fibrillation	
		Other cardiac dysrhythmia	
		Cardiac conduction disorders	
		Other CVD	
		COPD	
		Asthma	
		Obstructive sleep apnoea	
		Renal	
		Osteoarthritis	
		Rheumatoid arthritis	
		Dorsopathies	
		Fractures	
		Falls	
		Osteoporosis	
		Hypothyroidism	
		Hyperthyroidism	
		Other disorders of thyroid gland	
		Depression	
		Anxiety	
		Sleep disorders	
		Neoplasms	

BOEHRINGER INGELHEIM Group of Companies
Statistical and Epidemiological Analysis Plan (SEAP) for Non-Interventional Studies (NIS)

c37922104-02

Page 24 of 27

Proprietary confidential information © 2022 Boehringer Ingelheim International GmbH or one or more of its affiliated companies

		Human immunodeficiency virus infection Ulcerative colitis Crohn's disease Gastroesophageal reflux disease Gastrointestinal haemorrhage	
5	Use of insulin		
6	Use of other oral hypoglycaemic agents		
7	Use of drug(s) associated with acute pancreatitis *	α -methyldopa, azodisalicylate, bezafibrate, cannabis, carbimazole, codeine, cytosine, arabinoside, dapson, enalapril, furosemide, isoniazid, mesalamine, metronidazole, pentamidine, pravastatin, procainamide, pyritonol, simvastatin, stibogluconate, sulfamethoxazole, sulinda, tetracycline, valproic acid, all trans-retinoic acid, amiodarone, azathioprine, clomiphene, dexamethasone, ifosfamide, lamivudine, losartan, lynesterol/methoxyethinylestradiol, Mercaptopurine, meglumine, methimazole, nelfinavir, norethindronate/mestranol, omeprazole, premarin, sulfamethazole, trimethoprim-sulfamethazole, acetaminophen, chlorthiazide, clozapine, didanosine, erythromycin, estrogen, L-asparaginase, pegasparagase, propofol, tamoxifen, azathioprine, sulfonamides, tetracyclines, alpha-methyldopa	
8	Use of any other medications not mentioned above	
 • Agents acting on the renin-angiotensin system • Antibacterials for systemic use • Antidepressants 	

BOEHRINGER INGELHEIM Group of Companies
Statistical and Epidemiological Analysis Plan (SEAP) for Non-Interventional Studies (NIS)

c37922104-02

Page 25 of 27

Proprietary confidential information © 2022 Boehringer Ingelheim International GmbH or one or more of its affiliated companies

		
 • Antiepileptics • Antiinflammatory and antirheumatic products • Antineoplastic agents • Antipsoriatics • Antithrombotic agents • Beta-blocking agents • Calcium channel blockers • Diuretics • Drugs for acid-related disorders • Drugs for obstructive airway diseases • Immunosuppressants • Lipid-modifying agents • Opioids • Psycholeptics • Psychostimulants, agents used for ADHD, and nootropics 	
9	History of acute pancreatitis risk factors	
 • Abdominal surgery • Alcoholism • Cystic fibrosis • Gallstones and other gallbladder and biliary tract disorders • High calcium levels in the blood (hypercalcemia) • Hyperparathyroidism • Hypertriglyceridemia • Infection • Injury to the abdomen • Lupus • Liver disease • Pancreatic disease 	
Codes are listed in the following excel file:
  
1245-0201%20Code s%20part%204%20-%

10	Lab test results (when available)	
 • amylase (U/L); • lipase (U/L); • white cell count (G/L); • red cell count (T/L); • haemoglobin (g/L); • haematocrit (%); • thrombocyte (G/L); • C-reactive protein (mg/L); • creatinine (μmol/L), 	

BOEHRINGER INGELHEIM Group of Companies
Statistical and Epidemiological Analysis Plan (SEAP) for Non-Interventional Studies (NIS)

c37922104-02

Page 26 of 27

Proprietary confidential information © 2022 Boehringer Ingelheim International GmbH or one or more of its affiliated companies

		
carbamid (mmol/L); serum bilirubin (μmol/L);
 
• GGT (mmol/L);• GOT (mmol/L);• GPT (mmol/L);• ALP (mmol/L);• uric acid (mmol/L);• cholesterol (HDL, LDL) (mmol/L); triglycerides (mmol/L);• serum protein (g/L);• albumin (g/L),• C-peptide (pmol/L);• HgbA1C (%);• OGTT test glucose (mmol/L) and insulin level (pmol/L) at 0, 60 and 120min [add reference].• HbA1c (%)• LDL level (mg/dl)• HDL level (mg/dl)• Total cholesterol (mg/dl)• Triglyceride level (mg/dl)• Creatinine (mg/dl)• BUN (mg/dl)• BNP• NT-proBNP• Lipase	
11	Procedures	
• Abdominal ultrasound	

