### **9.3.2      Outcomes**

#### **9.3.2.1      Primary outcomes**

In this study we will use a modified version of an algorithm developed and validated in the [REDACTED] with a sensitivity of 89.8% and a specificity of 79.4% [[R20-3555](#), [R20-3554](#)]. In the original algorithm, only the Logical Observation Identifiers Names and Codes (LOINC) were used for the lipase measurement but since these codes are only available for a subset of patients in Marketscan and Optum databases, to accommodate database needs, the equivalent Current Procedural Terminology (CPT) codes were added to the algorithm. This modified algorithm is:

- The presence of an acute pancreatitis diagnosis from any of the inpatient (not restricted to the primary diagnosis), outpatient, or emergency contacts diagnoses (ICD-9-CM 577.0 or ICD-10-CM K85)  
AND
- A lipase measure within +/- 7 days of the acute pancreatitis diagnosis (using LOINC code of 3040-3 and 2572-6 or CPT code of 83690 for lipase)  
AND
- An abdominal ultrasound (using CPT codes of 76700 and 76705) within +/- 7 days of the acute pancreatitis diagnosis

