For a subset of about 40-50% of patients in Optum Clininformatics and 5-15% in MarketScan, laboratory test results are available through linkage with two nationally operating lab test provider chains. Available laboratory test results during the 6 months prior to the index date will be identified using LOINC codes. After PS matching, if major imbalance is observed, patient characteristics with and without lab test results might be further explored as optional additional analysis.

In case of multiple values available for a specific lab result, we will only consider the closest to the date of drug initiation. Laboratory tests of interests are provided in [Annex 5](#) and include amylase (U/L); lipase (U/L); white cell count (G/L); red cell count (T/L); haemoglobin (g/L); haematocrit (%); thrombocyte (G/L); C-reactive protein (mg/L); creatinine ( $\mu$ mol/L); urea (mmol/L); serum bilirubin ( $\mu$ mol/L); GGT (mmol/L); GOT (mmol/L); GPT (mmol/L); ALP (mmol/L); uric acid (mmol/L); cholesterol (HDL, LDL) (mmol/L); triglycerides (mmol/L); serum protein (g/L); albumin (g/L); C-peptide (pmol/L); HgbA1C (%); OGTT test glucose (mmol/L) and insulin level (pmol/L) at 0, 60 and 120 min [\[R20-3572\]](#).

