## **9.4 DATA SOURCES**

Two large US claims databases (Truven Marketscan Commercial Claims and Encounters (CCAE), Truven Marketscan Medicare Supplemental (MDCR), and Optum Clininformatics® Data Mart [CDM]) will be used in this study. Meta-analysis of the 2 databases might be used, when appropriate, to achieve the required study size.

Main data elements from each database that will be used in this analysis include: 1) enrolment records, 2) pharmacy dispensing claims (dispensing date, National Drug Code [NDC] to determine product prescribed, quantity, and days of supply, and 3) medical claims (service date, diagnosis codes [ICD-9-CM, ICD-10-CM], procedure codes [Current Procedural Terminology (CPT)-4, ICD-9 Procedure Coding System (PCS), ICD-10-PCS], and laboratory test results (when available).

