Given that MarketScan and Optum CDM are claims databases, clinical laboratory data is only available for a small portion of enrollees (approximately 40-50% in Optum CDM and about 5% in [REDACTED] MarketScan).

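### Prior lipase testing enters the covariate list only as a lab result that most patients lack, so it cannot be balanced or checked directly, although the outcome already uses a claims code for the same test

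*SAP*

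**What the plan says.** - **Baseline lipase.** SAP Annex 3 names lipase twice, once with units and once without, both times in row 10, headed "Lab test results (when available". Row 11, Procedures, has one entry: "Abdominal ultrasound".
- **How baseline labs are found.** Protocol 9.3.3: "Available laboratory test results during the 6 months prior to the index date will be identified using LOINC codes". On coverage: "For a subset of about 40-50% of patients in Optum Clininformatics and 5-15% in MarketScan, laboratory test results are available through linkage". Protocol 9.9.1 gives a lower MarketScan figure: "approximately 40-50% in Optum CDM and about 5% in" MarketScan.
- **Lipase in the outcome.** Protocol 9.3.2.1 requires a diagnosis code, a lipase test and an abdominal ultrasound, each test within 7 days of the diagnosis. Lipase is identified "using LOINC code of 3040-3 and 2572-6 or CPT code of 83690 for lipase". The CPT code was added to the LOINC codes "since these codes are only available for a subset of patients in Marketscan and Optum databases".
- **Data elements.** Protocol 9.4 lists, among the main elements of the medical claims, "procedure codes [Current Procedural Terminology (CPT)-4".
- **Missing values.** Protocol 9.7.7 and SAP 9.2 give a variable that is missing for some patients a missing category.
- **Use of the covariates.** Protocol 9.3.3 says that some of the listed covariates enter the propensity score, without saying which. Protocol 9.7.2 tabulates balance and considers further adjustment where a standardized difference exceeds 10%.

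**The concern.** A patient becomes a case only if a lipase test and an ultrasound are done, so the outcome depends on who is worked up. A recent lipase test before the index date plausibly marks abdominal symptoms, suspected biliary or pancreatic disease, and a provider's readiness to order the test that the outcome needs. If its frequency differs between the matched arms, the hazard ratio can shift through true risk and through detection. Protocol 9.9.3 accepts that lipase and ultrasound may be ordered to rule pancreatitis out and so inflate incidence, and Protocol 9.9.2 expects channelling between the arms.

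The plan solves the coverage problem for the outcome and leaves it in place for the covariate. A patient with a billed lipase test before index but no linked lab result looks the same as a patient never tested. Matching cannot act on the difference, and the balance table cannot show it.

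**Working it through.** **1. The plan's own figure.** The plan gives no number on this point. Its only calculated figure is the sample size. The Farrington-Manning formula for a risk ratio (0.0022 in both arms, ratio 1.5, one-sided alpha 0.05, power 80%, 1:1) returns 34,585.4 per group and 69,170.8 overall, as stated. Nothing below changes it.

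**2. Who lacks a lab result.** Inputs are the Protocol 9.3.3 percentages.
- Optum: 100% minus 40-50% = 50-60%.
- MarketScan: 100% minus 5-15% = 85-95%. The 5% in Protocol 9.9.1 lies at the edge of this range.
- Pooled, with w the assumed Optum share: lacking = 1 - [w × Optum coverage + (1 - w) × MarketScan coverage].

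| Assumed Optum share | Lacking lab results |
|---|---|
| 25% | 76-86% |
| 50% | 68-78% |
| 75% | 59-69% |

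At least half lack results under any mix.

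**3. What the missing category does.** For lipase it merges linked patients who were not tested, unlinked patients who were not tested, and unlinked patients who were tested and billed. Only patients both tested and linked stand apart.

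**4. What the balance table would show.** Assume that linkage does not depend on arm or on testing, and let c be the captured share. Testing frequencies p and q then appear as cp and cq. The standardized difference is (p - q) / √{[p(1 - p) + q(1 - q)] / 2}. The value c = 27.5% is the midpoint of 22.5-32.5%, the pooled coverage at an equal database mix. The testing frequencies are assumptions.

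| Tested, one arm v other | All tests seen | c = 27.5% | c = 5% |
|---|---|---|---|
| 5% v 3% | 0.102 | 0.053 | 0.022 |
| 8% v 4% | 0.169 | 0.086 | 0.037 |

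For 4% v 2% the values are 0.117 with all tests seen and 0.061 at c = 27.5%. In each case a difference above the 10% flag appears below it.

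**5. Illustrative effect on the hazard ratio.** Let p1 and p0 be the proportions tested in the empagliflozin and comparator arms, and RR the pancreatitis rate ratio for tested against untested patients. All three are assumptions. The factor is [1 + p1(RR - 1)] / [1 + p0(RR - 1)].
- 2% v 3%, RR 3: 1.04 / 1.06 = 0.981
- 3% v 5%, RR 5: 1.12 / 1.20 = 0.933
- 2% v 4%, RR 5: 1.08 / 1.16 = 0.931

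With the arms exchanged the factors are 1.019, 1.071 and 1.074. The range is about 0.93 to 1.07, with no allowance for covariates correlated with lipase testing.

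**The case against.** **Much of prior work-up is already covered.** A reader might infer that matching cannot balance prior pancreatic work-up at all. The documents do not support that. Annex 3 lists abdominal ultrasound, gallstones and other biliary disorders, hypertriglyceridemia, alcoholism, abdominal surgery and injury, and liver disease. Protocol 9.2.2 excludes anyone with pancreatic disease recorded at any time before the index drug was started. This stands: the gap is prior lipase testing itself, net of these proxies. However, since only some covariates enter the propensity score, even ultrasound is not certain to be matched on.

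**Detection has a planned check.** The first sensitivity analysis in Protocol 9.7.6 uses the primary hospital discharge diagnosis alone, with no lipase or ultrasound requirement. If lipase ordering drove the result through the algorithm, the two definitions should tend to diverge. This stands in part: the analysis does not adjust for baseline testing or for the underlying risk that testing may mark.

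**The imbalance may be small.** In the 2% v 3% scenario the standardized difference is only 0.064 with every test seen, so the plan's 10% rule would not flag it. That is fair, although entering the variable in the propensity score would still help.

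**CPT capture is not complete.** That the code is seen for every patient is an inference. Protocol 9.9.1 ties capture to a claim being submitted, so unbilled tests stay hidden.

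**The code lists cannot be seen.** Rows 10 and 11 show no codes, and the embedded code files are not visible. A CPT definition for the second lipase entry cannot be ruled out, but Protocol 9.3.3 points to LOINC.

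**Conclusion.** The point holds for prior lipase testing. As written, the plan leaves it without direct balance or a direct check for about 50-60% of Optum and 85-95% of MarketScan patients, while the outcome uses a claims code that avoids most of the same gap. The coverage figures come from the protocol. That CPT reaches nearly all billed tests is inferred from Protocol 9.3.2.1 and 9.4.

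The size and direction of residual bias cannot be derived from the documents. The factors of 0.93 to 1.07 depend on assumed testing frequencies, arm differences and rate ratios, and correlated covariates would be expected to reduce them.

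A reader might go further and infer an inflated chance of wrongly excluding a ratio of 1.5. With 34,585.4 × 0.0022 = 76.1 events per arm, the standard error of the log hazard ratio is √(2/76.1) = 0.162. Then Φ(-1.645 - ln(factor)/0.162) gives 6.3%, 11.1% and 11.4% for the three downward factors, against 5%. The arithmetic is sound, but it requires more baseline testing in the sulfonylurea arm, and the documents give no reason to expect that. With the imbalance reversed, the error falls below 5%. This should not be presented as a finding.

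**What to change.** 1. Add to SAP Annex 3, row 11: lipase test performed in the look-back (CPT 83690 or LOINC 3040-3 / 2572-6), yes/no.
2. State that this indicator and abdominal ultrasound both enter the propensity score and the balance table, in both databases.
3. Keep the numeric lipase result as a descriptive item for the lab-linked subset.

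The cost is one extra binary covariate. The codes are already specified for the outcome, and no new data or change in sample size is needed. The remaining limit is that a test is seen only if it was billed or has a linked result.
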